#### SAMPLE SIZE CALCULATIONS

Sample size was calculated using data from Tanaka et al., who showed a reduction in fluid volume requirements in burn patients (a marker of vascular permeability) of 46% (5.5 ml/kg vs. 3.0 ml/kg indexed by burn size) associated with vitamin C treatment (10). We have recently found an average ECS on the first day following delivery of 13 (with a standard deviation of  $\pm$  7) in patients with severe features of preeclampsia not treated with vitamin C (6). To discern a decrease of 46% in ECS between the study (vitamin C) and placebo groups we would require a minimum sample size of 17 patients per group, which was calculated using a desired power of 0.80 and an alpha of 0.05.

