#### STUDY OUTCOME

The primary outcome studied will be the Echo Comet Score (ECS) at days 1, 2, and 3 following delivery in the vitamin C vs. placebo group. Mann Whitney U-test will be used for comparing ECS between the two study groups (vitamin C vs. placebo)

Lung ultrasound assessment will be performed once daily in the first three days following delivery. The amount of EVLW will be determined by the ECS obtained by summing the number of B-lines or "comet tails" found on each of the 28 chest wall areas. In addition to the 28 region technique, the ECS using the more clinically applicable 8 anterior region technique will also be documented.

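### Seventeen per group gives 0.80 power only under assumptions the plan does not declare; two-sided with SD 7 in both arms, 22 to 24 per group are needed

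*Combined protocol and SAP*

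**What the plan says.** The section SAMPLE SIZE CALCULATIONS holds the only justification of the trial's size. The baseline comes from the sponsor's earlier work: "We have recently found an average ECS on the first day following delivery of 13", with SD 7, "in patients with severe features of preeclampsia not treated with vitamin C". The target is "To discern a decrease of 46% in ECS between the study (vitamin C) and placebo groups", a percentage borrowed from fluid requirements in a burns trial. The plan concludes that it would "require a minimum sample size of 17 patients per group, which was calculated using a desired power of 0.80 and an alpha of 0.05".

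The section STUDY OUTCOME names the analysis: "Mann Whitney U-test will be used for comparing ECS between the two study groups (vitamin C vs. placebo"). It also defines the endpoint: "The primary outcome studied will be the Echo Comet Score (ECS) at days 1, 2, and 3 following delivery". The score is "obtained by summing the number of B-lines" over 28 chest wall areas, so it is a non-negative count.

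Neither section says whether the test is one- or two-sided, what SD is expected under vitamin C, what shape the scores are assumed to have, or which formula gave 17.

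**The concern.** A reader who sees alpha 0.05 with no sidedness will usually assume a two-sided test, and will apply the only SD given to both arms. On that reading 17 per group does not reach 0.80 power, so either the claim is too high or it rests on something not written down.

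Two things are at stake. The first is how a null result can be read. If true power were 0.65, a real 46% reduction would be missed about 35% of the time (1 − 0.65), not the 20% that the plan implies. The second is that undeclared sidedness leaves the significance threshold of the primary test open until analysis.

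**Working it through.** **Inputs.** From SAMPLE SIZE CALCULATIONS: control mean 13, SD 7 (untreated patients), reduction 46%, alpha 0.05, power 0.80. From STUDY PROTOCOL: 1:1 allocation. From STUDY OUTCOME: Mann-Whitney test. The difference is Δ = 0.46 × 13 = 5.98, so the vitamin C mean is 7.02 and the standardised difference is 5.98/7 = 0.854.

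**Step 1: reproduce 17.** The normal formula with a common SD is n = 2σ²(z_α + z_β)²/Δ². One-sided at 5%, SD 7 in both arms:

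2 × 49 × (1.645 + 0.842)² / 5.98² = 16.94, rounded up to 17.

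The plan's figure is therefore reproducible. One-sided, the t-test needs 17.66 (18), and the Mann-Whitney test on normal scores needs 19.

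**Step 2: the same inputs, two-sided.**

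- Normal formula: 2 × 49 × (1.960 + 0.842)² / 5.98² = 21.51, so 22 per group.
- t-test: 22.51, so 23.
- Mann-Whitney: 22.51/0.955 (its efficiency relative to the t-test on normal data) = 23.57, so 24. Simulated power is about 0.79 at 23 and 0.80 at 24.

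Two-sided power at 17 per group:

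- Normal formula: Φ(5.98/(7√(2/17)) − 1.960) = Φ(0.531) = 0.70.
- t-test: 0.68.
- Mann-Whitney, by simulation on normal scores: about 0.65.

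**Step 3: the other routes to 17.** With SD s in the vitamin C arm, the two-sided normal formula is (1.960 + 0.842)²(49 + s²)/5.98². It is just over 16 at s = 4.89, 16.55 at s = 5.14 and just under 17 at s = 5.33, so any s in that interval rounds up to 17. A common SD of about 6.2 also gives 17. The plan states none of these SDs.

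**Step 4: the planned test at 17 per group.** Mann-Whitney power by simulation (20,000 to 200,000 trials per row). Every distribution is my assumption; the plan gives none.

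| Assumed scores | Two-sided | One-sided |
|---|---|---|
| Normal, SD 7 in both arms | 0.65 | 0.76 |
| Normal, vitamin C SD 5.33 | 0.75 | 0.84 |
| Normal, vitamin C SD 4.89 | 0.77 | 0.86 |
| Normal, vitamin C SD 3.78 (= 7 × 0.54) | 0.82 | 0.89 |
| Negative binomial, shifted down 6 | 0.71 | 0.81 |
| Gamma, shifted down 5.98 | 0.73 | 0.83 |
| Negative binomial, vitamin C mean 7.02, SD 7 to 4.19 | 0.80 to 0.82 | 0.88 to 0.90 |
| Gamma, vitamin C mean 7.02, SD 7 to 3.78 | 0.82 to 0.85 | 0.90 to 0.92 |

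On normal data, the one-sided route of step 1 gives the planned test 0.76, and the vitamin C arm SD route of step 3 gives 0.75 to 0.77 two-sided. Neither reaches 0.80.

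**Step 5: detectable effect.** With normal scores, SD 7 in both arms and a two-sided test, 17 per group reaches 0.80 power for a reduction of about 55%.

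**The case against.** **The figure 17 is reproducible.** This stands. A reader might infer a calculation error, but the one-sided normal formula gives 16.94 from the stated mean, SD, percentage, alpha and power. The objective is also worded as a reduction, which is compatible with a one-sided test. It does not declare one, though, and that formula does not size the Mann-Whitney test.

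**The 0.65 comes from an implausible model.** This also stands in part. A normal vitamin C arm with mean 7.02 and SD 7 puts 16% of scores below zero, which a count cannot take. Flooring at zero and rounding leaves power at about 0.64 to 0.65, but it moves the means to 13.10 and 7.61, a 42% reduction, so it is not the power for 46%.

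**A percentage effect suggests proportional scaling.** If scores shrink by the factor 0.54, the vitamin C SD is 3.78. The two-sided normal formula then gives 13.89 (14 per group), and Mann-Whitney power at 17 is about 0.82. That reading is reasonable and makes 17 sufficient, but the plan does not state it.

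**Skewness rescues the claim.** Only sometimes. Skewed shapes with the treated mean moved to 7.02 within the same family give 0.80 to 0.85. The same shapes shifted down by about 6 points give 0.71 to 0.73. How the effect acts on the scores matters as much as their shape.

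**Seventeen is called a minimum.** Enrolment may be larger, but the 0.80 is claimed for 17.

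**Conclusion.** The point holds as a gap between a stated power and the inputs stated for it. Two-sided at 0.05 with SD 7 in both arms, the plan needs 22, 23 or about 24 per group. At 17 its power is 0.70 (normal formula), 0.68 (t-test) or about 0.65 (Mann-Whitney on normal scores), against the claimed 0.80. Reaching 17 takes an undeclared one-sided test or an undeclared smaller SD.

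A reader might go further and conclude that the trial is underpowered or must enrol 24 per group. The documents do not support that. The 0.65 depends on normal scores with equal SDs, while ECS is a non-negative count of unstated shape. Two-sided power over the cases tried runs from about 0.65 to 0.85. These are the range tried, not limits.

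Confidence is high that the assumptions are undeclared and that the ordinary two-sided, equal-SD reading falls short. It is not high for any single power figure. All of these figures concern day 1, whereas the primary outcome also covers days 2 and 3.

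**What to change.** In STUDY OUTCOME, state that the Mann-Whitney test is two-sided at 0.05. If a one-sided test was intended, declare and justify it.

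In SAMPLE SIZE CALCULATIONS, replace the 0.80 claim with wording such as:

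> With 17 patients per group and SD 7 in both arms, the two-sided Mann-Whitney test on day-1 ECS has about 65% power for a 46% decrease if scores are roughly normal; 80% power is reached for a decrease of about 55%.

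If a smaller vitamin C arm SD, proportional scaling or a skewed count distribution was assumed, state and justify it, and give the resulting power instead. The sponsor's earlier day-1 scores can supply the shape: resample them, with the treated arm scaled by 0.54 or shifted by 5.98 points, and report which was used. Say that the figure applies to day 1 only.

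The cost is two short protocol edits and, if needed, one short simulation. No extra patients are required. The downside is that the stated power may become less favourable, and declaring the test two-sided gives up the higher one-sided power.
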